9.1 Dropout

A subject is considered to have “dropped out” of the study if they are randomized but later decide to discontinue participation. Because of the potential compliance issues in postpartum patients and possible side effects of the drugs, we anticipate a dropout of 10%. Participants will be asked in the consent form to allow follow-up via medical records after they drop out. Every effort will be made to ask subjects to complete a withdrawal form, which will allow us to learn more about why the subject chose to leave this study. As with crossover patients, all patients who drop out of the study will be included in the analysis on an intention to treat principle.

7.2 Analysis plan

Aim 1: Analysis of the primary outcome will be performed assessing rates of willingness to participate and patient retention in the study for 42 days postpartum. Secondary outcome measures will be attrition rate and compliance rates to both care and medication.

Aim 2: We will be developing an ROC curve with Youden’s index to predict the optimum SBP and DBP from intrapartum and postpartum to target for postpartum blood pressure thresholds for blood pressure management to prevent postpartum readmission due to severe hypertension.

Aim2-8: Baseline demographic and descriptive statistics will be compared to assess comparability of the study groups. Continuous variables will be assessed with student t-test and categorical data will be analyzed using ANOVA.

Aim 4: Analyses were performed to determine whether it is cost-effective to use Bluetooth-enabled tablets for postpartum blood pressure monitoring in comparison to standard monitoring in women with hypertension-related disorders of pregnancy. The data for the analyses will be derived from a prospective study at UnityPoint Health- Meriter Hospital where patients with hypertensive-related disorders of pregnancy will be enrolled in either standard management of blood pressure (routine nurse blood pressure visit 3-5 days from discharge) or monitoring with a Honeywell Genesis Android Touch Bluetooth remote patient monitoring system. Primary outcomes examined will include cost and readmissions.

8. Feasibility

Table #. UnityPoint Health-Meriter Data 2015. Total deliveries: 3873

Hypertensive disorder	Maternal (n=476)	Neonatal (n=147)
Chronic	87 (18%)	30 (20%)
Gestational, preeclampsia and SIPE	387 (81%)	115 (78%)
Eclampsia	2 (0.4%)	2 (1.4%)

** We anticipate that we will have approximately 40 patients with a hypertension related disorder for potential enrollment each month. At the beginning of the study, we only had 30 mobile health units that could have been used at any time. Effective 10/01/2017, an additional 10 mobile health units were acquired, making 40 mobile health units to available for study use at any time. We would strive to include all in the future as routine care if possible. We believe this project will be very successful in improving the quality of care for postpartum women at risk of developing severe complications associated with hypertension.

** The initial phase study is reasonable to complete in 1 year. Estimating a total of 400 patients annually with a hypertensive related disorder. Only 14% of the hypertensive patients would be required to participate.

**We had access to 30 mobile health units at the beginning of the study, and in 1 year that would allow for participation from 220 patients if we were using all units on a rolling basis (20 new recruits per month). Effective 10/01/2017, we now have access to 40 mobile health kits, in which we will not change the sample size, but will achieve 220 participants more quickly.

** To maximize patients eligible for recruitment I am reaching out to all obstetrical providers. I have approval to recruit patients who receive their primary obstetrical care from the Perinatal Center and the UW Health General Obstetrics clinics. I will be meeting with the private practitioner groups to assess their willingness to utilize this program with their patients prior to approaching their patients for enrollment.

9. Cost determination

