1.3 Motivation for this study

Hospital readmission was more common in patients with mild hypertension prior to their primary delivery discharge. In addition, Hirshberg, et al discovered postpartum patients were less likely to be readmitted due to hypertension related complications if they were discharged on antihypertensive medication therapy. Treatment or surveillance strategies have been understudied for postpartum patients with hypertension. Demonstration of a decrease in hospital readmission with a novel mobile application may provide an effective method of preventing severe maternal postpartum hypertension related hospital readmission and associated maternal morbidities.

2. Objectives

Aim 1: Conduct an initial phase study for postpartum women at risk for severe hypertension to estimate the rates of willingness to participate in and utilize remote mobile health applications to monitor home blood pressures and weights, medication adherence after hospital discharge, to inform a trial to decrease postpartum maternal morbidity and readmission.

Sub Aim 1: Conduct a survey regarding patient satisfaction using mobile health technology

Hypothesis: We hypothesize that the mobile health application will be implemented with strong fidelity, have positive patient acceptability, and demonstrate a meaningful reduction in home blood pressures and postpartum hospital readmission.

Aim 2: Obtain prospective daily monitoring of blood pressures in the Peripartum period (initial hospital admission through 6 weeks postpartum) to understand natural history of development and resolution of postpartum hypertension using all patients utilizing the mobile health program over year 1. Specifically, this data will be used to estimate standard deviations of SBP and DBP in the intrapartum compared to 24-96 hours postpartum to inform a future trial regarding the threshold blood pressure to prevent development of severe hypertension or hospital readmission.

Hypothesis: We hypothesize women with severe intrapartum hypertension will predict development of severe hypertension within 7 days of delivery more often than blood pressures obtained in the first 24-96 hours after delivery.

Aim 3: Compare the maternal outcomes in the cohort utilizing remote patient monitoring to the cohort of patients with hypertension related disorders discharged with routine care. This would include all patients from Aim 1 as well as the remaining from the entire 1-year experimental period.

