Concerning vital signs are SBP ≥ 150 or DBP ≥ 100 or SBP ≤ 90 or DBP ≤ 60 , which is the same as prior to discharge from the hospital. After the program began using the above paragraph which outlines need for medication initiation or management – it was acknowledged patients were requiring the initiation and management of their vital signs or medications often, i.e. approximately 40-50% of the patients. Therefore, the mobile health nurses needed a written document with the standard practice to determine the thresholds patients would need to initiate or titrate medications up or down. Therefore we developed algorithms as proposed in this modification that would help manage this care. In addition, as needed the patient will be instructed to call their provider as needed for any concerning vital signs or symptoms if the nurses are not available or as needed. If the patient does not have any concerning symptoms the abnormal vital signs will be discussed with the patient by the patient's provider or the nurse. If the patient is asymptomatic then there is the ability to refer to the management algorithm and then initiate medication or increase/decrease the dose of the medication per the algorithm. The algorithm is based off the standard of care – it is just to ease the communication and care coordination of the patients. The mobile health nurse will notify a doctor with initiation of medication.

It is expected that the patients with gestational hypertension or preeclampsia diagnoses will be able to titrate off of the antihypertensive medication between 14 -42 days postpartum. The recommendation to discontinue the antihypertensive medication can be performed if the patient has (SBP ≤ 120 or DBP ≤ 80) by the 14-day follow-up visit. If they are unable to do so by the 42-day follow-up visit they will likely be diagnosed with chronic hypertension (persistent elevation of blood pressure SBP ≥ 140 or DBP ≥ 90 by 12 weeks postpartum. It is expected that patients with chronic hypertension may need to continue this therapy beyond the study endpoint of 42 days.

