7.1. Sample size calculation

Aim1:

Our sample size calculation is based on numerous assumptions.

To estimate rates of participation and retention a sample size of 50 subjects we will be able to estimate a participation rate of 80% to within a 95% confidence interval of $\pm 10\%$ and a retention rate of 60% to within a 95% confidence interval of $\pm 13\%$.^{13,14,15,16} Adjusting for up to a 10% drop out rate we increased the sample size to 55 subjects.

Aims 2-5; are not powered as they are exploratory outcomes that will be used for future study planning. However, there may be up to 440 subjects available to include in this analysis. This was determined knowing there are 30 mobile units available at all times. The endpoint is at 6 weeks. So, this would allow for 30 patients in the first month and then on a rolling basis approximately 20 patients could be recruited per month at max enrollment. This would total 220 patients using mobile health for the 1-year experimental period. The control group would be subjects matched within the same month of experimental subjects and be a 1:1 matching. So the control group would consist of up to 220 patients. The numbers may be less due to lower rates of recruitment/participation.

Aim 7-8:

The original study is closed to accrual, with a total of 214 subjects enrolled. With the success of the study, UPH-Meriter decided to incorporate the home monitoring program into its standard clinical services as of January 1, 2019. Through UPH-Meriter, 358 patients received services through this clinical program.

We would like to retrospectively review the patient data in Peridata for these 358 patients. We will collect home vital sign data to assess blood pressure trends from early pregnancy through pregnancy and postpartum. This additional data would help to increase our sample size in this evaluation. The same data would be collected from the clinical patients.

Therefore, our sample size would increase. We enrolled 214 subjects in the original Telehealth study, with 214 matched controls. 358 patients received remote monitoring services from the UPH-Meriter program. 100 providers with delivery privileges at UPH-Meriter were offered the opportunity to complete a survey regarding the research. The new sample size is 886 patients. We do have prior IRB approval to collect data from Peridata for our original study patients.

1. Non-compliance policies

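### Aim 2's Youden cut-offs for SBP and DBP have no interval, no optimism correction and no rule for combining the two pressures

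*Combined protocol and SAP*

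**What the plan says.** Section 7.2 (Analysis plan), Aim 2, is a single sentence. An ROC curve with Youden's "index to predict the optimum SBP and DBP from intrapartum and postpartum to target for postpartum blood pressure thresholds" is to guide blood pressure management, the purpose being "to prevent postpartum readmission due to severe hypertension". Nothing is said about the expected number of readmissions, an interval for either cut-off, validation, or how an SBP cut-off and a DBP cut-off become one rule. It also does not say which measurement window supplies the pressures; Appendix I lists maxima for labor and several periods after delivery.

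Other places bear on this:

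- Section 2, Aim 2, defines the population as "using all patients utilizing the mobile health program over year 1". Section 7.1 projects its size: "This would total 220 patients using mobile health for the 1-year experimental period". The same section reports actual accrual: "We enrolled 214 subjects in the original Telehealth study, with 214 matched controls".
- The Aim 2 hypothesis in section 2 names a different outcome. Severe intrapartum hypertension "will predict development of severe hypertension within 7 days of delivery".
- Section 7.1 limits the ambition: "Aims 2-5; are not powered as they are exploratory outcomes that will be used for future study planning".
- Blood pressure rules elsewhere join the two pressures by *or*. Under the follow-up procedures in section 6: "Concerning vital signs are SBP ≥ 150 or DBP ≥ 100". Section 1.1 and the opening of section 6 use the same form, the latter at both 140/90 and 150/100.

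**The concern.** The cut-off is itself a product of Aim 2: section 2 says the aim is to inform a future trial's threshold. Two things can go wrong with a bare Youden point.

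First, the maximum of an empirical ROC curve is the peak of a step function. With few events the peak moves a long way between samples. The sensitivity and specificity read off there are too favorable, because the same women chose the point.

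Second, accuracy belongs to a specific rule. Figures for SBP alone and DBP alone do not describe a rule that acts when either is exceeded.

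A later trial could therefore inherit a threshold without knowing that the data could not distinguish it from levels already in use, together with accuracy figures that will not be reproduced.

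**Working it through.** **Figures in the plan.** Section 7.1's 220 device users follow from 20 per month × 11 months = 220; the text read literally (30 in the first month, then 20 per month) would give 30 + 11 × 20 = 250. The difference does not matter here, because 214 were enrolled. No event count, precision or power is stated for Aim 2, so there is nothing further to reproduce.

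**Inputs.** From the documents: n = 214; SBP levels of 140 and 150 as a yardstick for precision. Assumed, because the documents give no value: readmission rate 3%, 5% or 10% (214 × 0.03 ≈ 6, 214 × 0.05 ≈ 11, 214 × 0.10 ≈ 21 events); SBP normal with mean 140 and SD 12 mmHg in women without the event; AUC 0.70; the same SD in women with it.

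**Target under these assumptions.**

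- Separation: √2 × Φ⁻¹(0.70) = 1.414 × 0.524 = 0.742 SD, or 8.9 mmHg.
- True optimum: 140 + 8.9/2 = 144.4 mmHg.
- Sensitivity = specificity = Φ(0.742/2) = Φ(0.371) = 0.645.
- Best attainable J = 2 × 0.645 − 1 = 0.289.

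**Sampling behavior of the empirical Youden cut-off.** Simulated studies of 214 women, pressures rounded to 1 mmHg, cut-off at the maximum of Se + Sp − 1. Each chosen cut-off is then scored on the true distributions. Repeated runs agree to about 1 mmHg and 0.01 in J.

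| Events | 95% range of SBP cut-off | SD | Outside 140-150 | Apparent J | True J at that cut | Excess |
|---|---|---|---|---|---|---|
| 6 | 131-162 | 7.4 | 44% | 0.45 | 0.25 | 0.20 |
| 11 | 133-159 | 6.4 | 38% | 0.40 | 0.26 | 0.14 |
| 21 | 135-156 | 5.3 | 30% | 0.37 | 0.27 | 0.10 |

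The ranges are 31, 26 and 21 mmHg wide, against 150 − 140 = 10 mmHg.

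**Dependence on the assumptions.** With 2-17 events in 214 and AUC 0.65-0.80, the 5-95% range is 15-34 mmHg wide. At AUC 0.70, all 428 women with 34 events give 135-151 (16 mmHg), and a commoner outcome of 20% in 214 (43 events) gives 136-151 (15 mmHg). These three checks used a true optimum of about 142 at AUC 0.70, so compare widths rather than positions.

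**The *or* rule, with no sampling error.** Let each pressure have AUC 0.70, each be cut at its own optimum, and their correlation r be the same in both groups. With Φ₂ the bivariate normal distribution function:

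- Specificity = Φ₂(0.371, 0.371; r)
- Sensitivity = 1 − Φ₂(−0.371, −0.371; r)

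| r | Sensitivity | Specificity | J |
|---|---|---|---|
| one pressure alone | 0.645 | 0.645 | 0.289 |
| 0.5 | 0.799 | 0.490 | 0.289 |
| 0.6 | 0.782 | 0.508 | 0.289 |
| 0.7 | 0.762 | 0.527 | 0.289 |

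Specificity falls by 12-15 points and sensitivity rises by the same amount. A larger sample does not change this.

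**The case against.** The strongest reply is that Aim 2 is openly exploratory and unpowered, and that a Youden point is a conventional summary for such work. That stands as a reason not to ask for more patients or a power calculation. It does not explain giving a threshold without an interval when the stated use is to plan the next trial.

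A reader might also infer more than the documents support:

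- *That readmissions are few.* No rate is given; the event counts here are assumptions.
- *That the plan commits to separate, empirical curves and an* or *rule.* Section 7.2 is silent on all three. Separate empirical curves are the ordinary reading of the sentence; the *or* form comes from the care rules elsewhere.
- *That the cut-offs are mostly noise.* Their median is within about 2 mmHg of the optimum, and J is flat near its peak. The chosen cut keeps about 85% (6 events) to 92% (21 events) of the attainable 0.289. The scatter in mmHg is real; the loss in classification is modest.
- *That joining by* or *makes the rule worse.* It trades specificity for sensitivity with J unchanged. The fault is only in letting single-marker figures stand for the rule.

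**Conclusion.** The point holds as a reporting and analysis gap in section 7.2, and it is cheap to close. Under an assumed 3-10% event rate, SBP SD of 12 and AUC of 0.70, the cut-off cannot separate 140 from 150 mmHg, and apparent J is too high by about 0.20 to 0.10. The width finding held in every scenario tried, from 2 to 43 events. The *or* result assumes equal AUCs and a correlation of 0.5-0.7, and applies only if the cut-offs are used in that form.

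The documents do not support saying that Aim 2 will yield a worthless threshold. Nor does this point bear on which blood pressure level is right. The size of the problem depends on the event count, which cannot be settled until sections 2 and 7.2 name the same outcome.

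**What to change.** In section 7.2, Aim 2, keep the ROC and Youden analysis and add:

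1. One named outcome, reconciled with the section 2 hypothesis (severe hypertension in the first week, or readmission), and the number of events observed.
2. Bootstrap 95% intervals for each cut-off.
3. Bootstrap optimism-corrected AUC and J, repeating the whole cut-off selection in every resample, including the choice of window if the data make it.
4. How SBP and DBP combine, with sensitivity and specificity of that rule as it would be used.
5. A statement that cut-offs are hypothesis-generating if their interval spans both 140 and 150 or the AUC interval includes 0.5.

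A logistic cut, taken where fitted risk equals the event rate, looks steadier but should not be substituted. With no association at all (AUC 0.50) and 6 events, it still gave a range of about 139-146 mmHg whenever the slope was positive. A useless marker would then appear precise.

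Cost: wording and a few hours of analysis, with no new data. Reported accuracy will be lower. At very low event counts the bootstrap removes only part of the optimism, and its interval for the peak of a step function is approximate.

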APPENDIX I

Data variables to extract from EPIC Electronic Medical Records/Peridata

1. Medical record number for mother
2. Date of birth
3. Link baby to mother (Medical record number)
4. Date of birth

Demographics Maternal

5. Maternal age
6. Tobacco use
 - a. Yes
 - b. No
7. Date of first prenatal care visit
8. Body mass index at first prenatal care visit
9. Body mass index at delivery or with initial admission
10. Body mass index at second admission
11. Body mass index >30 at delivery
 - a. Yes
 - b. No
12. Maternal weight in kilograms with first prenatal care visit
13. Maternal weight in kilograms on initial admission
14. Maternal weight in kilograms within 24 hours of delivery
15. Maternal weight in kilograms within 24-48 hours of delivery
16. Maternal weight in kilograms within 48-72 hours of delivery
17. Maternal weight in kilograms within 72-96 hours of delivery
18. Maternal weight in kilograms within 24 hours of initial admission discharge
19. Maternal weight in kilograms on readmission
20. Maternal weight in kilograms on discharge from readmission
21. Maternal diabetes
 - a. Gestational
 - b. Type 1
 - c. Type 2
22. Marital status
 - a. Married
 - b. Single
 - c. Unknown
23. Insurance
 - a. Commercial
 - b. Medicaid
 - c. HMO
 - d. Uninsured
 - e. Other
 - f. Unknown
24. Race

- a. Caucasian
- b. Hispanic
- c. African American
- d. American Indian/Alaskan Native
- e. African
- f. Asian American
- g. Other
- h. Unknown

25. Ethnicity

- a. Hispanic

26. Gravidity

27. Parity (live children)

28. Gestational age rounded in weeks at delivery

29. Estimated date of delivery

30. Singleton pregnancy

- a. Yes
- b. No

31. Multiple pregnancy

- a. Twins
- b. Triplets

32. Mode of delivery

- a. Normal spontaneous vaginal delivery
- b. Operative delivery
 - i. Forceps
 - ii. Vacuum
- c. Cesarean section

33. Indication for cesarean section

- a. First stage arrest
- b. Second stage arrest
- c. Fetal intolerance of labor
- d. Fetal distress
- e. Repeat cesarean section
- f. Failed trial of labor after prior cesarean section
- g. Elective primary cesarean section
- h. Vaginal bleeding/abruption
- i. Placentation
- j. Fetal malpresentation
- k. Maternal illness
- l. Other

34. Hypertension related disorder was diagnosed in pregnancy

- a. Prior to initial admission
- b. Prior to delivery of baby (intrapartum)
- c. After delivery of baby (postpartum)
- d. Only upon readmission to hospital after initial admission discharge

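### The plan assigns ANOVA to categorical data and names no categorical test; run on category codes, its p-value depends on how the levels are numbered

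*Combined protocol and SAP*

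**What the plan says.** Section 7.2 (Analysis plan) gives one rule for all group comparisons under Aims 2-8. It opens with the purpose: "Baseline demographic and descriptive statistics will be compared to assess comparability of the study groups". It then names the tests: "Continuous variables will be assessed with student t-test and categorical data will be analyzed using ANOVA". The only other statistical method named in that section is the ROC curve with Youden's index for Aim 2, which is not a group comparison of categorical data.

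Section 7.1 describes the groups. For the controls: "The control group would be subjects matched within the same month of experimental subjects and be a 1:1 matching". On enrolment: "We enrolled 214 subjects in the original Telehealth study, with 214 matched controls. 358 patients received remote monitoring services from the UPH-Meriter program". It also says that Aims 2-5 "are not powered as they are exploratory outcomes that will be used for future study planning".

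Appendix I lists the variables to be extracted. Several are unordered with more than two levels: marital status (item 22, 3 levels), insurance (item 23, 6), race (item 24, 8) and mode of delivery (item 32, 3 main levels). The plan does not say how such categories would be entered into an ANOVA.

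**The concern.** ANOVA compares the mean of a numeric response between groups. An unordered category has no mean. The sentence can be taken in two ways, and each needs correcting.

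1. **ANOVA on category codes.** The levels are numbered 1, 2, 3 and so on, and the mean code is compared between cohorts. The numbering is arbitrary, and so is the p-value.
2. **A drafting slip.** ANOVA may have been meant for continuous variables, for example across three cohorts. The plan then names no test for categorical data, and the analyst chooses one with the data in hand.

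This matters because the controls are not randomised and calendar month is the only matching factor stated. The tests in section 7.2 are the plan's only stated check that the groups are comparable. On the first reading, a real imbalance in delivery mode or insurance could be reported as absent because of how the levels happened to be numbered. Six-week feeding status (Appendix I, item 53, three levels), which serves Sub-Aim 5C, falls under the same sentence. Its levels could be regarded as ordered, so the order problem is less clear there.

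**Working it through.** The plan has no figure of its own to reproduce, because no sample size or power depends on this sentence.

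**Inputs.** Group size is 214 per group (section 7.1), and the numbers of levels come from Appendix I. Two inputs are assumptions: two-sided alpha of 0.05, since the plan states none for these comparisons, and all cell counts, since the documents give none.

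**Step 1: one table worked through.** Assume mode of delivery (vaginal/operative/cesarean) is 126/20/68 in one group and 107/44/63 in the other.

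Chi-square: with equal groups the expected counts are the column averages, 116.5, 32 and 65.5. The deviations are 9.5, 12 and 2.5.

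χ² = 2 × (9.5²/116.5 + 12²/32 + 2.5²/65.5) = 2 × (0.775 + 4.500 + 0.095) = 10.74 on 2 df, p = 0.005. This does not depend on level order.

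ANOVA on codes: F = (214/2) × (difference in mean code)² / pooled variance, on 1 and 426 df.

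| Codes (vaginal, operative, cesarean) | Mean codes | Pooled variance | F | p |
|---|---|---|---|---|
| 1, 2, 3 (listed order) | 370/214 = 1.729; 384/214 = 1.794 | 0.796 | 0.575 | 0.45 |
| 2, 1, 3 | 476/214 = 2.224; 447/214 = 2.089 | 0.429 | 4.59 | 0.033 |
| 1, 3, 2 | 322/214 = 1.505; 365/214 = 1.706 | 0.530 | 8.15 | 0.005 |

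Reversing an order changes nothing, so the six orders give three distinct p-values. In listed order the excess of operative deliveries (44 vs 20) sits in the middle code and barely moves the mean.

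**Step 2: other assumed tables, 214 per group.**

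| Counts | Chi-square p | ANOVA p: listed order; codes 2, 1, 3; codes 1, 3, 2 |
|---|---|---|
| 130/20/64 vs 112/40/62 | 0.018 | 0.38; 0.098; 0.011 |
| 124/18/72 vs 112/34/68 | 0.059 | 0.67; 0.13; 0.053 |

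In the second of these the verdict at 0.05 is the same under every order. The smallest expected counts in the three tables are 32, 30 and 26, so chi-square is valid for all of them.

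A six-level example (110/20/60/10/10/4 vs 110/35/35/10/15/9) gives chi-square p = 0.018. Over its 720 code orders ANOVA runs from 0.0003 to 1.00, with 35% of orders below 0.05.

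**Step 3: power without choosing counts.** Set the imbalance so that chi-square has 80% power. The non-centrality is then 9.63 (2 df), 12.83 (5 df) or 14.35 (7 df). ANOVA on codes is a 1-df test that receives the share cos²θ of it, where θ is the angle between the imbalance and the code vector. Averaging over uniformly distributed directions:

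| Levels | Chi-square power | ANOVA, average | ANOVA, range by direction |
|---|---|---|---|
| 3 | 80% | 52% | 5% to 87% |
| 6 | 80% | 32% | 5% to 95% |
| 8 | 80% | 28% | 5% to 97% |

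For some directions ANOVA beats chi-square. Multinomial simulation at 214 per group agreed: ANOVA 0.52, 0.32 and 0.28 against chi-square 0.81 in each setting. With no imbalance both tests reject 5% of the time, so the loss is in detection and not in false positives.

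**Step 4: two-level variables.** There is no order problem here. For 15 vs 30 events of 214, ANOVA and chi-square both give p = 0.018. With expected counts below 5, the verdict at 0.05 differs from Fisher's exact test in three splits only: 0 vs 4 (ANOVA 0.045, Fisher 0.12), 0 vs 5 (0.0245, 0.061) and 1 vs 7 (0.032, 0.068).

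**The case against.** The strongest reply is that a harmless setup exists. ANOVA ordinarily takes a categorical variable as the factor. With the category as factor and cohort membership (0/1) as response, the p-value does not depend on code order and tracks chi-square: 0.0045, 0.0178 and 0.0594 on the three delivery tables, against 0.0047, 0.0180 and 0.0594. That is correct, but the plan describes no such analysis, and it reverses outcome and group.

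Nothing in the plan shows that codes would be treated as numbers, and a drafting slip fits the text equally well. That stands. It is why the code-order problem is stated conditionally, and a slip still leaves categorical data without a named test.

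The counts are invented, and the uniform average over directions has no basis in the documents. Both points stand as limits on the size of the effect; the mechanism needs neither. The eight-level simulation used equal levels, which race is unlikely to have. With rare levels, chi-square itself may need replacing by an exact test.

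A test across all three cohorts is not explicitly planned, since Aims 7 and 8 are called descriptive. That also stands. The three cohorts serve here only as a possible explanation of why ANOVA was mentioned.

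Finally, the consequences are modest, and a marked imbalance would normally show in the tabulated percentages whatever the p-value. This limits the weight of the point but does not make the sentence right.

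**Conclusion.** The concern holds. The sentence is wrong as written, and an analyst cannot both follow it and run a standard categorical test. If it is applied to codes of unordered variables with three or more levels, the result depends on numbering. Average power falls from 80% to about 52%, 32% or 28% at 3, 6 or 8 levels, assuming 214 per group, alpha of 0.05 and no preferred direction of imbalance. If ANOVA was meant for continuous data, the defect is an unspecified test.

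The reach is the baseline comparability check and other unordered multi-level comparisons. Readmission and other two-level outcomes are nearly unaffected unless events are sparse. Aims 2-5 are exploratory and unpowered, no decision rule uses these p-values, and no sample size changes. It should be fixed, but it does not threaten the study's main comparisons. That no categorical test is named was checked only in the text available; section 7.2 itself appears complete.

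**What to change.** Replace the sentence in section 7.2 with: *Categorical variables will be compared by chi-square test, or Fisher's exact test when any expected count is below 5; continuous variables by Student's t-test between two groups, or ANOVA across three or more groups.*

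For feeding status, state whether the levels are treated as ordered and name the test accordingly. Whether the 1:1 month matching enters the outcome analysis is a separate question; it does not make unpaired baseline tests wrong.

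The replacement costs one sentence of wording, with no new data and no change in sample size.
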